#### **5.13.2.20. Treatment of Overdose**

Listing of patients reporting AEs related to over dosing of tirzepatide will be provided as a protocol deviation.

#### **5.13.3. Renal Safety**

A subpopulation of “Patients with T2DM and renal dysfunction” is of study interest, will be identified as  $eGFR < 60 \text{ mL/min/1.73m}^2$  or  $UACR > 300 \text{ mg/g}$  at baseline. The following analyses will be done in this subpopulation:

Summary and change from baseline in  $eGFR$  will be analyzed in MMRM analysis using actual measurements. The same analysis will be done for  $UACR$  in log scale. The analysis will be conducted utilizing for changes from baseline through post-baseline with a MMRM using restricted maximum likelihood (REML). The model will include stratification factors (country/pooled country, baseline  $HbA1c$  ( $\leq 8.5\%$ ,  $> 8.5\%$  [ $\leq 69$ ,  $> 69 \text{ mmol/mol}$ ]), baseline SGLT2 inhibitor use (Yes or No)), treatment group, visit, and treatment-by-visit interaction as fixed effects, and baseline value of the corresponding renal marker (log scale if the corresponding renal parameter is analyzed on the log scale) as a covariate.

Shift table for  $eGFR$  and  $UACR$  will be done in the renal dysfunction subpopulation. Treatment-emergent adverse events in the renal dysfunction subpopulation will be summarized by treatment using MedDRA PT nested within SOC. Serious adverse events in the renal dysfunction subpopulation will be provided. Analyses of changes from minimum baseline value to minimum postbaseline value will be performed for  $eGFR$ . Analyses of changes from maximum baseline value to maximum postbaseline value will be performed for  $UACR$ , Calcitonin, ECG parameters and vitals (pulse, SBP and DBP). Severe hypoglycemia and level 2 hypoglycemia events will be summarized by treatment, excluding hypoglycemia events occurring after initiation of rescue therapy. Post-baseline threshold analysis will be done for  $eGFR$  ( $< 15$ ,  $< 30$ ,  $< 45$ , and  $< 60$ ) and “ $eGFR < 60$  or  $UACR > 300$ ”.

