7.7. Concomitant Therapy

Patients will be permitted to use concomitant medications that they require during the study, except certain medications that may interfere with the assessment of efficacy and safety characteristics of the study treatments. Prohibited medications include GLP-1 receptor agonists, amylin agonists, and DPP-4 inhibitors. The list of excluded medications and procedures is provided in the Manual of Operations. Other medications for glycemic control for patients meeting severe persistent hyperglycemia criteria for rescue may be added during the study at the investigator's discretion. Patients on the insulin glargine arm should receive other antihyperglycemic medication only when further dose adjustment of glargine cannot control the persistent hyperglycemia.

Short-term insulin use is allowed for certain clinical situations (for example, elective surgery, during hospitalization, hyperosmolar states). Rescue therapy with other glucose-lowering agents, including basal or rapid acting insulins, may be medically indicated in certain situations after randomization due to severe, persistent hyperglycemia or early discontinuation of study treatment. If insulin is prescribed as a rescue therapy, it must be differentiated from short-term use of insulin therapy for medical emergencies when reported in the eCRF.

Investigative site staff will inform patients that they must consult with the investigator or a designated site staff member upon being prescribed any new medications during the study. This may not be possible when initiated for treatment of medical emergencies, in which case, the patient will inform the investigator or a designated site staff member as soon as possible. Any additional medication initiated during the course of the study (including OTC drugs, such as paracetamol or aspirin) must be documented, and the name of the drug and the date(s) of administration must be recorded on the "Concomitant Medications" section of the eCRF.

All nonstudy medications will be recorded on the eCRF at all visits.

Nonstudy medications taken by patients who are screened but not randomized will not be reported to Lilly unless an SAE or AE occurs that the investigator believes may have been caused by a study procedure.

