8.1. Discontinuation from Study Treatment

8.1.1. *Permanent Discontinuation from Study Treatment*

Possible reasons leading to permanent discontinuation of investigational product:

- **Patient Decision**
 - The patient requests to discontinue investigational product.
- **Discontinuation due to a hepatic event or liver test abnormality.** Patients who are discontinued from investigational product due to a hepatic event or liver test abnormality should have additional hepatic safety data collected via the electronic case report form (eCRF).

Discontinuation of the investigational product for abnormal liver tests **should be** considered by the investigator when a patient meets one of the following conditions after consultation with the Lilly designated medical monitor:

- ALT or aspartate aminotransferase (AST) >8X ULN
- ALT or AST >5X ULN for more than 2 weeks
- ALT or AST >3X ULN and total bilirubin level (TBL) >2X ULN or international normalized ratio (INR) >1.5
- ALT or AST >3X ULN with the appearance of fatigue, nausea, vomiting, right upper-quadrant pain or tenderness, fever, rash, and/or eosinophilia (>5%)
- alkaline phosphatase (ALP) >3X ULN
- ALP >2.5X ULN and TBL >2X ULN
- ALP >2.5X ULN with the appearance of fatigue, nausea, vomiting, right quadrant pain or tenderness, fever, rash, and/or eosinophilia (>5%)
- In addition, patients will be discontinued from the investigational product in the following circumstances:
 - If a patient is inadvertently enrolled and it is determined that continued treatment with study drug would not be medically appropriate (see Section 8.1.3)
 - Acute or chronic pancreatitis
 - If a patient is diagnosed with MTC after randomization
 - If a patient is diagnosed with an active or untreated malignancy (other than basal or squamous cell skin cancer, in situ carcinomas of the cervix, or in situ prostate cancer) after randomization
 - Any significant study drug-related hypersensitivity reaction
 - Any other TEAE, SAE, or clinically significant laboratory value for which the investigator believes that permanent study drug discontinuation is the appropriate measure to be taken

- If female patient becomes pregnant
- If a patient is diagnosed with T1DM

Patients who stop the study drug permanently may receive another glucose-lowering intervention (Section 7.4.2) and will continue participating in the trial according to the protocol to collect all planned efficacy and safety measurements.

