### **Study Period IV (safety follow-up period)**

Safety follow-up (Visit 801) visits:

All patients who complete the treatment period are required to complete Visit 801, a safety follow-up visit approximately 4 weeks after their last visit. Patients discontinuing the study early and performing an early termination (ET) visit will also be asked to perform the safety follow-up visit, so that the safety follow-up visit will be their final visit. During the safety follow-up period, patients will not receive study drug. Patients will be treated with another glucose lowering intervention decided upon by the investigator. Initiation of new antihyperglycemic therapy for the safety follow-up period will not be classified as “rescue therapy.”

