**Table GPGM.5.1. Analysis Populations/Data Sets**

Population/Data Set	Description
Screened population	All participants who sign informed consent
Randomized population	All patients who are randomly assigned a treatment arm
Modified intent-to-treat (mITT) population	All randomly assigned participants who are exposed to at least 1 dose of study drug.
Efficacy analysis set (EAS)	Data obtained during Study Period II and III from mITT, excluding patients discontinuing study drug due to inadvertent enrollment and data after initiating rescue antihyperglycemic medication or discontinuation of study drug (last dose date + 7 days).
Full analysis set (FAS)	Data obtained during Study Period II and III from mITT, excluding patients discontinuing study drug due to inadvertent enrollment, regardless of adherence to study drug or initiation of rescue antihyperglycemic medication.
Safety analysis set (SS)	Data obtained during Study Period II, III, and IV from mITT, regardless of adherence to study drug or initiation of new antihyperglycemic medication.

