### 5.13.2. Special Safety Topics

#### 5.13.2.1. Hypoglycemic Events

Definitions of different categories of hypoglycemic events are as follows:

	Symptoms and/or Signs of hypoglycemia	Blood Glucose Level
Glucose Alert Value:		
Documented symptomatic hypoglycemia	Yes	$\leq 70$ mg/dL (3.9 mmol/L)
Documented asymptomatic hypoglycemia	No	$\leq 70$ mg/dL (3.9 mmol/L)
Documented unspecified hypoglycemia	Unknown	$\leq 70$ mg/dL (3.9 mmol/L)
Clinically Significant Hypoglycemia:		
Clinically significant Documented symptomatic hypoglycemia	Yes	$< 54$ mg/dL (3.0 mmol/L)
Clinically significant Documented asymptomatic hypoglycemia	No	$< 54$ mg/dL (3.0 mmol/L)
Clinically significant Documented unspecified hypoglycemia	Unknown	$< 54$ mg/dL (3.0 mmol/L)
Severe Hypoglycemia		

**Severe hypoglycemia:** Defined as an episode with severe cognitive impairment requiring the assistance of another person to actively administer carbohydrate, glucagon, or other resuscitative actions. Severe hypoglycemia will be reported as a SAE. Severe hypoglycemia will be considered an adverse event of special interest (AESI).

**Nocturnal hypoglycemia:** Defined as any hypoglycemic event that occurs between bedtime and waking.

To avoid duplicate reporting, all consecutive hypoglycemic events in the same category, occurring within a 1-hour period may be considered to be a single hypoglycemic event.

Statistical summaries and analyses will exclude hypoglycemia events occurring after initiation of a new antihyperglycemic therapy. Severe hypoglycemia and hypoglycemia incidence (with blood glucose level  $\leq 70$  mg/dL [3.9 mmol/L] or  $< 54$  mg/dL [3.0 mmol/L], separately) as well as rate per patient year of exposure will be provided by treatment. The incidence of hypoglycemic event will be analyzed using logistic regression with treatment, country/pooled country, SGLT2i use at baseline (Yes/No) and baseline HbA1c ( $\leq 8.5\%$ ,  $> 8.5\%$  [ $\leq 69$ ,  $> 69$  mmol/mol]) as the fixed effects. The rate of hypoglycemic episodes per patient year will be analyzed using a generalized

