#### **5.13.2.2. Severe Persistent Hyperglycemia**

A summary or listing of initiation of rescue therapy in response to severe, persistent hyperglycemia will be provided by treatment. If there is sufficient number of episodes, time-to-first-event analysis for the initiation of rescue therapy will be conducted by treatment using Cox proportional regression model. A listing of patients initiating rescue therapy will be provided.

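### SAP 5.13.3 and 5.13.2.1 cut off hypoglycemia at different events, so the renal count can include follow-up events that the overall analysis excludes

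*SAP*

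**What the plan says.** The overall rule is in SAP 5.13.2.1: "Statistical summaries and analyses will exclude hypoglycemia events occurring after initiation of a new antihyperglycemic therapy". It is not limited to any population. It precedes the severe, ≤70 mg/dL and <54 mg/dL summaries and the incidence and rate models.

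The renal rule is in SAP 5.13.3. For patients with baseline eGFR below 60 or UACR above 300, severe and level 2 events are summarized by treatment, "excluding hypoglycemia events occurring after initiation of rescue therapy".

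Three other places bear on whether the two rules are the same:

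- SAP 4.1, Study Period IV: patients receive no study drug, and "Patients will be treated with another glucose lowering intervention decided upon by the investigator". On classification, "Initiation of new antihyperglycemic therapy for the safety follow-up period will not be classified as" rescue therapy.
- SAP Table GPGM.5.1, safety analysis set: "Data obtained during Study Period II, III, and IV from mITT, regardless of adherence to study drug or initiation of new antihyperglycemic medication".
- SAP 5.13.2.2 ties rescue to its indication: "initiation of rescue therapy in response to severe, persistent hyperglycemia".

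**The concern.** One SAP gives two stopping points for the same outcomes, with no reason for the difference. The unrestricted sentence in 5.13.2.1 also means that a programmer building the renal table has two instructions for it.

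What is at stake is whether the subgroup can be read against the whole. The SAP singles this subpopulation out as being of interest, and a reader will naturally set its hypoglycemia counts beside the overall ones. Under the current text, a patient's severe or level 2 event can appear in the renal table and be absent from the overall table. Because SAP 5.2 analyzes patients by randomized dose, such an event is attributed to the randomized arm although it occurred on a replacement regimen.

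**Working it through.** The plan gives no figure to reproduce. The check is a comparison of texts, followed by one share of follow-up time.

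**Step 1. Are the terms equal?** No. SAP 4.1 says that new antihyperglycemic therapy started for Period IV is not rescue. For that therapy, the 5.13.2.1 cut-off is triggered and the 5.13.3 cut-off is not.

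**Step 2. Is Period IV in the data?** Yes. The safety analysis set covers Periods II, III and IV. SAP 5.13 counts events up to the safety follow-up visit or end of participation. Protocol 9.2.2.1 collects hypoglycemia until the last study visit. SAP 5.13.3 states no narrower window.

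**Step 3. What happens to an event?** Outcome for a severe or level 2 event in a renal patient:

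| When the event occurs | Overall (5.13.2.1) | Renal (5.13.3) |
|---|---|---|
| Before any added or replacement therapy | counted | counted |
| After rescue for severe, persistent hyperglycemia | excluded | excluded |
| In Period IV, after replacement therapy starts | excluded | counted |
| After early drug discontinuation, on other therapy | excluded | depends on classification |

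The third row is a definite conflict.

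**Step 4. How long is that window?** Period IV is 4 weeks (Visit 801). Protocol 10.1 expects average follow-up of 18 to 22 months, which is 78 to about 95 weeks. Taking that as the treatment period and adding Period IV:

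- 18 months: 4 / (78 + 4) = 4 / 82 = 4.9%
- 22 months: 4 / (95 + 4) = 4 / 99 = 4.0%

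For individual treatment-period completers, the range is 4 / (52 + 4) = 7.1% at 52 weeks to 4 / (104 + 4) = 3.7% at 104 weeks. These are shares of follow-up time, not of events, and assume that replacement therapy starts at the beginning of Period IV.

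**Step 5. Early discontinuation.** Protocol 8.1.1 says: "Patients who stop the study drug permanently may receive another glucose-lowering intervention", and such patients stay in the trial. That wording and SAP 5.13.2.2 suggest that this therapy is not rescue. Protocol 7.7, however, describes rescue therapy as possibly indicated "after randomization due to severe, persistent hyperglycemia or early discontinuation of study treatment", which would make it rescue and close the gap. The documents do not settle the point. They also give no separate discontinuation rate, no timing, and no proportion starting another agent. No size can be computed for this row.

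**The case against.** The strongest reply is that 5.13.3 uses the protocol's own term. Protocol 10.3.4.1 repeats the hypoglycemia analysis with data after rescue therapy removed, and Protocol 10.3.4 speaks of excluding data on rescue therapy. On that view 5.13.2.1 is the section that departs. This stands in part: the documents do not say which cut-off is the intended one. It does not justify having both, because the protocol applies the rescue cut-off to a repeat of an all-data analysis, not to one subgroup.

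A second reply is that the wording is merely loose. SAP Table GPGM.5.1 describes the safety set as regardless of new antihyperglycemic medication, and SAP 5.13 describes it as regardless of rescue therapy. Interchangeable drafting is plausible as the cause, but SAP 4.1 makes the terms differ in effect for Period IV.

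A third is that keeping Period IV events is a defensible safety choice. Protocol 9.4.4 treats Visit 801 as the washout point, so tirzepatide exposure is declining over those weeks rather than absent. That is fair, but the reasoning applies equally to the overall table.

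A reader might also infer a much larger gap by treating all therapy after early discontinuation as non-rescue. The documents do not support a figure for that. Protocol 7.7 points the other way, and Protocol 8.1.1 says only that patients may receive other therapy. The 28% bound in Protocol 10.1 combines discontinuation with rescue, and rescued patients are cut off under both rules.

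**Conclusion.** The inconsistency is real and modest. For replacement therapy in Period IV, the two sections give opposite instructions, so the renal count need not nest within the overall count. The window is about 4% to 5% of follow-up time, assuming 18 to 22 months of treatment and replacement therapy from the start of the 4-week follow-up. No event rate is available to turn this into events. Any widening through early discontinuation is possible but conditional on classification, and is left unsized.

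A reader might go further and infer that the renal results are unusable, or that the tirzepatide–glargine contrast is materially distorted. The text does not support that. The renal item is a descriptive summary by treatment with no model, test or person-time, and the definite difference is confined to one short window. Primary and key secondary results are untouched. The case for acting is that the two stated rules conflict and aligning them costs very little.

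**What to change.** Apply one analysis cut-off to hypoglycemia in SAP 5.13.2.1 and 5.13.3. The simplest way is to reuse the 5.13.2.1 flag in 5.13.3, replacing the reference to rescue therapy with one to a new antihyperglycemic therapy. Define both terms once for analysis purposes, stating whether therapy begun in Period IV and therapy begun after drug discontinuation count, so that Protocol 7.7, Protocol 8.1.1 and SAP 5.13.2.2 are reconciled. If the all-data or rescue-only versions from Protocol 10.3.4.1 are kept, produce them for the overall and renal tables alike. If a different renal cut-off is intended, say so and give the reason.

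The cost is a phrase and a definition in the SAP. No new data are needed, and the existing flag can be reused. The downside is that a few events may drop from the renal table.

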- d) Age ≥ 50 years, history of CKD, and an estimated glomerular filtration rate < 60 mL/min/1.73m² (CKD-Epidemiology[CKD-EPI]) on consecutive measurements (Visit 1 and Visit 2)

OR

- e) Age ≥ 50 years and congestive heart failure (CHF) documented as a history of CHF by the New York Heart Association Functional Classification II to III

[5] Are of stable weight ($\pm 5\%$) ≥ 3 months prior to Visit 1 and agree to not initiate an intensive diet and/or exercise program during the study with the intent of reducing body weight other than the lifestyle and dietary measures for diabetes treatment

[6] Have a BMI ≥ 25 kg/m² at Visit 1

[7] Eighteen years or older at the time of signing informed consent

Male patients:

Male patients should be willing to use reliable contraceptive methods throughout the study and for at least 3 months after last injection

Female patients:

Female patients not of childbearing potential due to surgical sterilization (hysterectomy, bilateral oophorectomy, or tubal ligation) or menopause.

Women with an intact uterus are deemed postmenopausal if they are 45 years old, and

- have not taken hormones or oral contraceptives within the last year and had cessation of menses for at least 1 year

OR

- have had at least 6 months of amenorrhea with follicle-stimulating hormone (FSH) and estradiol levels consistent with a postmenopausal state (FSH ≥ 40 mIU/mL and estradiol < 30 pg/mL).

Female patients of childbearing potential (not surgically sterilized and between menarche and 1-year postmenopausal) must

- test negative for pregnancy at Visit 1 based on a serum pregnancy test

AND

- if sexually active, agree to use 2 forms of effective contraception, where at least 1 form is highly effective for the duration of the trial and for 30 days thereafter
- not be breastfeeding

[8] In the investigator's opinion, are well motivated, capable, and willing to

- perform SMBG (up to 7 measures in a day)
- learn how to self-inject treatment (LY3298176 or insulin glargine), as required for this protocol (visually impaired persons who are not able to perform the injections must have the assistance of a sighted individual trained to inject the study drug; persons with physical limitations who are not able to perform the injections must have the assistance of an individual trained to inject the study drug)
- are willing and able to inject study drug QW/once daily
- maintain a study diary, as required for this protocol

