### Revision History

SAP Version 1 was approved prior to the first patient receiving study drug.

SAP version 2 was approved prior to the interim cardiovascular (CV) meta-analysis and final database lock. The main changes of this version are:

1. Updated definition of analysis set: Per agreement with the US Food and Drug Administration (FDA), patients that discontinue study drug due to inadvertent enrollment are excluded from efficacy analyses.
2. Updated baseline definition for selected measures based on scientific consideration and to minimize missing values at baseline.
3. Updated primary endpoint: Missing data imputation. Corrected the definition of “retrieved dropout.” Use of local laboratory data for glycemic control measures when central laboratory data are not available.
4. Updated the language to handle lack of convergence in longitudinal logistic regression analysis due to low number of events for hemoglobin A1c (HbA1c) and weight loss target analyses.
5. Updated the language in section on adverse events of special interest and renamed section to “Special Safety Topics” to be consistent with the program SAP (see Section 5.13.2).
6. Updated the language in Section 5.13.2.1 to provide clarity on definitions of different categories of hypoglycemic events and analysis of hypoglycemic events.
7. Added Section 5.13.3 for additional analyses on renal safety based on a revised definition of renal impairment (eGFR<60 mL/min/1.73m^2 or UACR >300 mg/g at baseline).
8. Added language in Section 5.19.1 according to protocol amendment (b) for an interim data extraction to support the program wide interim cardiovascular safety meta-analysis.
9. Added Section 5.20 for COVID-19 impact assessment.

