#### **5.13.2.15. Acute Renal Events**

Laboratory measures related to renal safety will be analyzed as specified for laboratory measurements in Section 5.16.

Additionally, two shift tables examining renal function will be created. A min-to-min shift table of estimated glomerular filtration rate (eGFR) estimated by the Chronic Kidney Disease Epidemiology Collaboration (CKD-EPI) equation with units ml/min/1.73m^2, using categories (<30, ≥30 to <45, ≥45 to <60, ≥60 to <90, and ≥90 mL/min/1.73m^2). A max-to-max shift table of urine albumin-to-creatinine ratio (UACR), using the categories UACR<30 mg/g, 30 mg/g ≤ UACR ≤300 mg/g, UACR>300 mg/g (respectively, these represent normal, microalbuminuria, and macroalbuminuria).

The AE database will be searched using SMQs of acute renal failure and chronic kidney disease to identify events consistent with acute renal events. The incidence of the resulting TEAEs will be summarized by treatment and PT. Detailed searching criteria can be found in [Appendix 1](#). Severe/serious acute renal events will be considered as AESI.

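### SAP 5.13.3: the combined renal threshold repeats the criterion that selects the subpopulation, so that row cannot show new impairment

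*SAP*

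**What the plan says.** The SAP Revision History records that Section 5.13.3 was added in version 2 around a revised definition of renal impairment: eGFR <60 "or UACR >300 mg/g at baseline". Section 5.13.3 uses that definition to pick out a subpopulation and then states: "The following analyses will be done in this subpopulation".

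The list that follows contains:
- change in eGFR, which "will be analyzed in MMRM analysis using actual measurements", and the same for UACR on the log scale;
- eGFR and UACR shift tables, which "will be done in the renal dysfunction subpopulation";
- adverse events and serious adverse events;
- "Analyses of changes from minimum baseline value to minimum postbaseline value will be performed for" eGFR, with the maximum-to-maximum counterpart for UACR;
- the thresholds: "Post-baseline threshold analysis will be done for" eGFR <15, <30, <45 and <60, and the combination eGFR <60 or UACR >300.

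For the thresholds, the section does not say whether a patient must be on the other side of the cut-off at baseline. Nor does it say whether the count is over any visit, the last visit or each visit.

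Outside the subpopulation, SAP 5.13.2.15 says: "Additionally, two shift tables examining renal function will be created". One is for eGFR and one for UACR, with cut-points that include 60 and 300. The two markers are not combined.

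**The concern.** A threshold count is normally read as the number of patients who got worse. Here the last threshold is the condition that put the patients into the table, so a high percentage in every arm is expected whatever the treatment does. Similar percentages near the ceiling could be taken as a sign of no renal difference. The eGFR <60 threshold has the same weakness in milder form, because eGFR <60 is one of the two ways into the subpopulation.

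The patients in whom the combined criterion could newly appear are those who did not meet it at baseline, and they are outside this analysis. The plan has no new-onset analysis of the combination elsewhere. That matters because Protocol 9.2.2.11 names deterioration of renal function, through dehydration after gastrointestinal events, as a possible risk.

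The sentence also departs from the documents' habit elsewhere. Protocol 10.3.4.4 defines a treatment-emergent low laboratory value as a crossing from at or above the limit at baseline. SAP 5.13.2.3.1 and 5.13.2.6 tabulate pancreatic enzymes and calcitonin by baseline category.

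**Working it through.** The documents give no rate, count or power for this analysis, so there is no stated figure to reproduce. The main check is logical; the simulations only illustrate size.

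**1. Logic of the combined row.** Let C be the condition eGFR <60 or UACR >300. The subpopulation is everyone with C at baseline, so 100% meet C at baseline. Three counting rules are possible:
- *Any post-baseline visit.* A patient counts unless C is absent at every visit. With per-visit persistence p and independent visits, the share counted is 1 − (1 − p)^k. For p = 0.70 and k = 4 this is 1 − 0.30^4 = 0.992. Allowing latent within-patient correlation of 0 to 0.8 and p of 0.70 to 0.95, the simulated share is 85% to about 100% over 4 visits and 88% to about 100% over 6.
- *Treatment-emergent* (the Protocol 10.3.4.4 convention). The denominator is patients without C at baseline, which is zero here.
- *Single visit.* The row shows how many still meet C, that is, persistence or regression to the mean.

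None of these measures new impairment.

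**2. Patient-level illustration.** From the Schedule of Activities: eGFR at weeks 12, 24, 42 and 52, and UACR at weeks 42 and 52. Assumed, not from the documents: true eGFR with mean 78 and SD 22; UACR median 20 mg/g with log SD 1.6; eGFR measurement CV of 5%, 8% or 12%; UACR log error SD 0.5; mean eGFR slope of 0, −2 or −5 mL/min/1.73m2 per year with between-patient SD 4. Each setting has 400,000 simulated patients before selection.

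Over all nine settings, 91–96% meet C at any visit to week 52, and 75–92% at week 52 alone.

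Share of the whole subpopulation meeting each threshold at any visit, CV 8%:

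| Threshold | slope 0 | slope −5 |
|---|---|---|
| eGFR <60 or UACR >300 | 92.7% | 95.3% |
| eGFR <60 | 81.0% | 84.5% |
| eGFR <45 | 38.1% | 48.8% |
| eGFR <30 | 8.3% | 12.5% |
| eGFR <15 | 1.1% | 2.0% |

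**3. The eGFR <60 row.** Over all settings it runs at about 80–85%. Only patients with baseline eGFR of 60 or more can newly cross, about 16–17% of the simulated subpopulation, all of whom qualified by UACR.

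**4. At-risk denominators.** With only patients at or above the cut-off at baseline counted (CV 8%, slope 0 against −5), new eGFR <45 goes from 17.2% to 30.3% and new eGFR <30 from 3.0% to 7.0%. These rows carry information inside the subpopulation.

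**5. Does the combined row respond at all?** A second simulation used eGFR mean 75–80 and SD 20–22, visit SD 4–8, UACR median 30 mg/g, both markers at 4 visits, and any-visit counting. A fall of 3 mL/min/1.73m2 in every patient moved the combined row from 0.950, 0.931, 0.960 and 0.918 to 0.969, 0.956, 0.976 and 0.944 in four settings. Among patients without C at baseline, new onset moved from 0.201, 0.173, 0.156 and 0.212 to 0.254, 0.219, 0.210 and 0.263.

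Standardised difference = (p2 − p1)/√[p̄(1 − p̄)], where p̄ is the mean of p1 and p2. First setting: inside, 0.019/√(0.9595 × 0.0405) = 0.096; outside, 0.053/√(0.2275 × 0.7725) = 0.126. Over the four settings the inside values are 0.091–0.108 and the outside values 0.116–0.140. The inside/outside ratio is 0.65–0.93.

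**The case against.** A reader might infer that renal worsening cannot be seen in this subpopulation. The documents do not support that. Section 5.13.3 itself plans the repeated-measures models, the shift tables, the minimum and maximum changes, adverse events and the three lower eGFR thresholds, all of which can show worsening. Section 5.13.2.15 adds shift tables not limited to the subpopulation, in which new onset of each component is visible; only the union is missing.

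A reader might also infer that nearly every patient in every arm is sure to be counted. That depends on an any-visit rule the SAP does not state and on distributions it does not give; the week-52 range above is well short of a ceiling at its lower end. If the treatment-emergent convention of Protocol 10.3.4.4 was meant to apply, the lower eGFR rows already have at-risk denominators, though the SAP does not say so.

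Nor can it be said that the combined row is unable to detect any change. Step 5 shows that it keeps 65–93% of the standardised difference of the new-onset analysis. Its fault is what it measures, not complete insensitivity.

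Finally, patients entering under Protocol inclusion criterion 4d ("history of CKD, and an estimated glomerular filtration rate" below 60 at Visits 1 and 2) do not meet a post-baseline outcome by design. Two low screening values make persistence likely, but a later value can be 60 or above. This is also one of five risk routes, and its share is not given.

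All of this stands and limits the point. It leaves untouched the identity between the combined threshold and the selection criterion.

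**Conclusion.** The concern holds in limited form. The combined row cannot show new impairment under any counting rule; this follows from the text and needs no assumption. The eGFR <60 row is weak, because it is open to new crossings only in patients who qualified by UACR alone. The <45, <30 and <15 rows are usable but underspecified.

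The percentages rest on assumed eGFR and UACR distributions, measurement error and slopes, and should be read as illustration only.

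The consequence is small: one uninformative row, one weak row and a missing new-onset analysis of the combination, in a descriptive safety section without multiplicity control. The renal safety assessment as a whole is not lost. Correction is still worthwhile because the section was added specifically for this definition of renal impairment and the remedy is cheap.

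**What to change.** Amend the threshold sentence in SAP 5.13.3 as follows:
- Remove eGFR <60 or UACR >300 from the subpopulation analysis. Report it as new onset among safety-set (mITT) patients who do not meet it at baseline.
- In the subpopulation, report each eGFR threshold (<60, <45, <30, <15) only among patients at or above it at baseline. For <60 this means patients who qualified by UACR alone.
- State the counting rule, for example any post-baseline visit.

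This takes one or two sentences and uses data already collected. The cost is smaller denominators for each threshold, most of all for <60.
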